### 1.2. Secondary Objectives

1.2.1. To examine the impact of an eHealth intervention for insomnia on the clinical severity of insomnia symptoms in adult survivors of childhood cancer.

Hypothesis 1.2.1.: A larger proportion of survivors randomized to the CBTi intervention will no longer meet clinical criteria for insomnia post-intervention compared to survivors randomized to online patient education.

1.2.2. To determine whether treatment of insomnia symptoms will improve neurocognitive function in adult survivors of childhood cancer with both insomnia and neurocognitive impairment.

Hypothesis 1.2.2.a.: Survivors randomized to an eHealth CBTi intervention will report significantly fewer symptoms of neurocognitive impairment post-intervention compared to survivors randomized to online patient education only.

Hypothesis 1.2.2.b.: Improvement in insomnia symptoms will mediate the association between intervention status (CBTi vs. online patient education) and improved neurocognitive function post-intervention.

Hypothesis 1.2.2.c.: Symptoms of emotional distress and cardiac health will be associated with improved insomnia symptoms and neurocognitive function.

1.2.3. To explore the mediating effects of improved neurocognitive function, emotional distress, and cardiovascular health on the association between insomnia symptoms and quality of life.

Hypothesis 1.2.3.a.: Survivors with improved insomnia symptoms following completion of an eHealth CBTi intervention will report better health-related quality of life compared to survivors without improved insomnia symptoms.

Hypothesis 1.2.3.b.: Neurocognitive function, symptoms of emotional distress, and biomarkers of cardiovascular health following completion of the eHealth CBTi intervention will mediate the association between improved insomnia symptoms and quality of life 6-months post-intervention.

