## 2.0 BACKGROUND AND RATIONALE

### 2.1. Background

**Childhood Cancer Survivors Are a Growing Population with a High Burden of Morbidity** - More than 80% of children diagnosed with a new cancer now survive five years, with most becoming long-term survivors. This has resulted in a growing population of childhood cancer survivors, estimated to approach half a million by 2020. Unfortunately, curative treatments also result in toxicities that leave many survivors with substantial burden of adverse physical and mental health outcomes. Morbidities commonly observed after cancer treatment include fatigue and sleep disturbance, neurocognitive impairment, emotional distress, cardiovascular disease, and diminished quality of life (QoL).

Defined as difficulty initiating or maintaining sleep, or nonrestorative sleep resulting in decreased daytime function, insomnia is the most commonly reported sleep disturbance among adults. In the general population, rates of insomnia range from 10 to 15%, with higher prevalence observed among women than men. Insomnia also impacts a substantial proportion of childhood cancer survivors. A recent report indicated that 28% of adult survivors of childhood cancer (excluding CNS tumor survivors) experience symptoms severe enough to warrant active treatment for insomnia. Compared to siblings, adult survivors of childhood cancer are significantly more likely to report poor sleep efficiency (PR=1.3; 95% CI, 1.-1.5), with one-third reporting delayed onset and less than 7 hours of sleep per night. Notably, sleep disturbances following treatment for childhood cancer are often present in adolescence and likely persist for decades into adult survivorship. It has been recently reported that approximately two-thirds of adolescent survivors of acute lymphoblastic leukemia (ALL) experience delayed sleep onset and 30-40% had frequent nighttime and premature awakenings. Insomnia has been associated with many of the late health complications observed in survivors of childhood cancer, including neurocognitive impairment, emotional distress, and cardiovascular disease. Because adult survivors of childhood cancer have been exposed to neurotoxic and cardiotoxic chemotherapies and radiation, their compromised cardiovascular and neurologic systems may be more sensitive to the effects of insomnia on neurocognitive and cardiac functions. Thus, there is not only a need

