## 2.2. Rationale

### Insomnia and Neurocognitive Morbidity

In non-cancer populations, insomnia has been associated with impaired cognitive performance, particularly in the domains of attention, memory, and executive function. A recent meta-analysis revealed moderate effects sizes for the impact of insomnia on episodic memory (ES = -0.51), problem solving (-0.42), and working memory (ES = -0.42). Working memory impairment has been observed on direct performance-based measures as well as through assessment of neural function via integrity of the hippocampus in adults with insomnia. Insomnia also has been associated with dementia in the general population and emerging evidence suggests that adult survivors of childhood cancer may experience accelerated cognitive aging. Using data from the Childhood Cancer Survivor Study (CCSS), we demonstrated that among adult survivors (n=1,426), after adjustment for neurotoxic therapies [e.g., cranial radiation], poor sleep quality is associated with impaired task efficiency (RR=1.23, 1.01-1.49) and memory (RR=1.45, 1.19-1.76); daytime sleepiness is associated with emotional regulation problems (RR=1.38, 1.14-1.67), diminished organization (RR=1.80, 1.31-2.48), and impaired memory (RR=2.05, 1.63-2.58). There are no data to suggest that neurocognitive deficits precede the onset of insomnia symptoms; however, sleep distribution has been shown to exacerbate neurocognitive deficits.

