### Theoretical Model

It has been established that childhood cancer and its treatment may result in symptoms of insomnia, neurocognitive impairment, emotional distress, and cardiovascular risks (Figure 2), and that these factors contribute to survivor QoL. We propose that insomnia may have an overarching impact on neurocognition, emotional distress, and cardiovascular health, consistent with observations from the general population, but that this impact may be particularly salient in survivors with compromised neurologic and cardiovascular systems related to prior cancer therapy. Using this model, we propose that insomnia may serve to exacerbate or maintain neurocognitive impairment, emotional distress, and cardiovascular risks in long-term survivors of childhood cancer, and that improved insomnia may serve to improve these late effects, ultimately improving survivor QoL. We recognize the potential for bidirectional influences among variables; however, based on past literature and the temporal developmental of late effects in childhood cancer survivors we propose to test our a priori hypothesized theoretical model.

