direct relationships between change in ISI (baseline to post-intervention) with emotional distress and cardiac health indices at postintervention time points and with HRQoL measures. To establish whether a mediation relationship exists, we will follow standard methodology by 1) establishing that there is an association between the causal variable (e.g. CBTi intervention) and the outcome (e.g. neurocognitive impairment), 2) establishing the association between the causal variable and the mediator and 3) showing that the mediator is associated with the outcome variable in a model with the causal variable included and 4) in the same model as used to evaluate step 3, determine that the relationship between the causal variable and the outcome variable is attenuated by inclusion of the mediator in the model. We do not expect to observe complete mediation in any of our investigations. Specifically, the above methodology will be used to test hypothesis 1.2.2.b with the causal variable defined as CBTi intervention, mediator as change in insomnia (ISI) and outcomes as neurocognitive indices. Hypothesis 1.2.2.c will consider change in insomnia as the causal variable, neurocognitive function indices, emotional distress symptoms and cardiovascular risk indices as mediators for the outcome HRQoL at 6 months. In addition to the stepwise model-based approach outlined above, we will also evaluate relationships using Structural Equation Modelling (SEM) approaches to evaluating mediation, which would allow simultaneous evaluation of the multiple pathways and classes of variables together in a single model, with improved power, allowing estimates of direct and indirect effects calculated from each. All effects size estimates (mean differences and/or odds ratios) will be presented along with associated confidence intervals and two-sided p-values, both unadjusted and adjusted for multiple comparisons. Primary therapies for childhood cancer have been associated with insomnia and study outcomes (neurocognitive morbidities, emotional distress, cardiovascular risk). Because our study inclusion criteria require that survivors have observed neurocognitive deficits we do not expect differential responses to SHUTi by previous childhood cancer treatment exposures. However, chemotherapy exposures and radiation doses are abstracted from medical records and cumulative doses of methotrexate (high dose and intrathecal), cytarabine, and cranial radiation will be included as covariates in relevant analyses. In addition, we will conduct sensitivity analyses to examine their contributions to treatment response.

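### The models with a cardiovascular mediator name no cardiotoxic dose as a covariate, which leaves the path from cardiovascular index to quality of life open to confounding

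*Combined protocol and SAP*

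**What the plan says.** The dose covariates are set in section 9.1, Statistical Analysis: "cumulative doses of methotrexate (high dose and intrathecal), cytarabine, and cranial radiation will be included as covariates in relevant analyses". The list is not worded as examples, and the plan does not define which analyses are relevant.

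Just before it, the same section says: "Primary therapies for childhood cancer have been associated with insomnia and study outcomes (neurocognitive morbidities, emotional distress, cardiovascular risk". It also says that "chemotherapy exposures and radiation doses are abstracted from medical records". Section 2.1 says of these survivors that, having been "exposed to neurotoxic and cardiotoxic chemotherapies and radiation, their compromised cardiovascular and neurologic systems may be more sensitive" to the effects of insomnia. The Theoretical Model in section 2.2 has cancer treatment leading to insomnia, neurocognitive impairment, distress and cardiovascular risk, and adds that "these factors contribute to survivor QoL".

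Hypothesis 1.2.3.b states that "biomarkers of cardiovascular health following completion of the eHealth CBTi intervention will mediate the association between improved insomnia symptoms and quality of life" at 6 months. Section 9.1 gives the matching model: change in ISI is the causal variable, the cardiovascular indices are among the mediators, and 6-month HRQoL is the outcome. It is to be fitted by a four-step procedure and by a structural equation model (SEM). Section 9.1 labels this model 1.2.2.c, whereas section 1.2 states it under 1.2.3.b; the label should be reconciled.

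**The concern.** The plan recognises that past therapy bears on cardiovascular risk, then names dose covariates that include no exposure identified as cardiotoxic. If a cardiotoxic dose worsens the cardiovascular index and also lowers HRQoL by some other route, the two will be associated even if the index has no effect on HRQoL.

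Randomisation gives no protection. It balances past dose between arms, but this model relates two post-randomisation measurements to each other and to a third. At stake is the interpretation of one secondary, exploratory objective (1.2.3): a cardiovascular-to-HRQoL path could be reported that partly reflects treatment received decades earlier.

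**Working it through.** **Does another planned adjustment cover cardiotoxic dose?**
- Stratification (section 3.5): sex, age and cranial radiation only.
- Adjustment for imbalance (9.1): concerns comparisons between arms.
- Treatment variables in the missing-data paragraph (9.1): sensitivity analyses for missing data only.
- Exposure sensitivity analyses (9.1): concern response to the intervention, not confounding of mediator and outcome.
- Baseline values of the index or of HRQoL: no such adjustment is stated for the mediation models in the text I could read. One sentence there is cut off at its start.

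None covers it.

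**Inputs for the illustration.** The plan states no figure for this path, so there is none to reproduce. From Power and sample size: 70 per sex per arm at 6 months, so 70 × 2 = 140 per sex and 70 × 4 = 280 in all. The test is two-sided at 0.05. Assumed, because the documents give no values: the dose has standardised effect *a* on the index M and *c* on HRQoL; ISI change X has effect 0.2 on each; the true effect of M on HRQoL is zero.

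**Formula.** Regressing HRQoL on M and X without the dose gives

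- expected coefficient b = ac / (1 − 0.2²) = ac / 0.96
- SE ≈ √[(0.96 − (ac)²/0.96) / (0.96 n)]
- rejection ≈ Φ(b/SE − 1.96) + Φ(−b/SE − 1.96)

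For a = c = 0.3 and n = 280: b = 0.09/0.96 = 0.094; SE = √(0.9516/268.8) = 0.0595; b/SE = 1.58; rejection about 35%.

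| a / c | b | Rejection, n=280: formula (simulated) | Rejection, n=140: formula (simulated) |
|---|---|---|---|
| 0.1 / 0.1 | 0.010 | 5.3% (4.9%) | 5.2% (4.8%) |
| 0.2 / 0.2 | 0.042 | 10.7% (10.6%) | 7.8% (8.0%) |
| 0.3 / 0.3 | 0.094 | 35.1% (35.0%) | 20.0% (20.8%) |
| 0.4 / 0.3 | 0.125 | 55.9% (56.2%) | 32.0% (32.4%) |

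Simulations used 4,000 runs per setting. A simpler version without X gave 9.3%, 31.8% and 53.9% at n=280 and 7.6%, 17.7% and 28.8% at n=140 for the last three rows. With the dose in the model, rejection was 4.6% to 5.4% throughout.

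**From this path to a mediation claim.** The table covers step 3 only (mediator associated with outcome, given the causal variable). Step 2 also requires ISI change to be associated with the index, and the omitted dose does not create that association. Simulating all four steps (3,000 runs, assumed effect of ISI change on HRQoL 0.3, n=280) gave:

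| Effect of ISI change on index | 0.2/0.2 | 0.3/0.3 | 0.4/0.3 |
|---|---|---|---|
| 0 | 0.4% | 1.1% | 1.5% |
| 0.1 | 3.6% | 14% | 22% |
| 0.2 | 11% | 32% | 53% |

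This follows from the power of step 2. At n=280 and effect 0.2, z = 0.2 × √280 / √0.96 = 3.42, power about 93%, and 0.93 × 35% ≈ 32%. At n=140 the same effect gives z = 2.42, power about 68%, and 0.68 × 21% ≈ 14%, so the by-sex rate stays well below step 3.

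**Baseline adjustment.** Adding the baseline index, with assumed stability 0.7, brought rejection back to 4.0% to 5.6% without the dose, provided the dose acts on the later index only through its baseline value.

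**The case against.** The strongest reply is that step-3 rates are not error rates for a mediation claim. That stands. A reader might infer from the table that the trial has a one-in-three or one-in-two chance of falsely declaring cardiovascular mediation. The four-step procedure does not support that unless ISI change truly moves the index.

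Second, the effect sizes are assumed, and at 0.1/0.1 there is no material inflation. The dose must also reach HRQoL outside the modelled variables. In a single SEM, neurocognition and distress sit beside the cardiovascular indices and would block part of the bias. This stands as a limit on size; the stepwise models lack that protection.

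Third, baseline adjustment alone could suffice if old exposures act only through baseline. That is plausible, but no such adjustment is stated, so it belongs in the fix.

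Fourth, a reader might say that the listed covariates are all neurotoxic. The documents do not go so far: they give cranial radiation as an example of a neurotoxic therapy ("after adjustment for neurotoxic therapies [e.g., cranial radiation") and do not classify methotrexate or cytarabine. What the text supports is narrower: no listed dose is identified as cardiotoxic.

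Finally, objective 1.2.3 is exploratory, the plan does not forbid further covariates, and p-values adjusted for multiplicity will be shown beside the nominal ones. These points lower the stakes. They do not put a cardiotoxic dose into the model, and choosing one after seeing the data would be worse than naming it now.

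**Conclusion.** The concern holds for the secondary, exploratory models with a cardiovascular mediator. The plan identifies the class of confounder, says that treatment doses are abstracted, and names covariates without it, so the index-to-HRQoL coefficient is open to confounding.

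Its size cannot be fixed from the documents. Under the stated assumptions it runs from nothing (dose effects 0.1/0.1) to step-3 rejection of 32-35% at n=280 and 18-21% at n=140 (0.3/0.3). A false four-step claim occurs in about 0.4-2% of trials at n=280 if ISI change is unrelated to the index, for dose effects of 0.2/0.2 to 0.4/0.3. It comes close to the step-3 rates only if that effect is about 0.2. The four-step figures do not cover the SEM, which was not simulated.

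A reader might also infer that the trial's main result is in doubt. It is not: the primary ISI comparison and the other contrasts between randomised arms do not depend on this adjustment.

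**What to change.** In section 9.1, keep the current dose list and define which analyses it applies to. For every model with a cardiovascular index as mediator or outcome, including the SEM, add:

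1. the abstracted cumulative cardiotoxic chemotherapy dose and heart-exposing radiation dose. Anthracyclines and chest radiation are examples; the documents do not name them, so the study team should confirm what has been abstracted;
2. the baseline values of the cardiovascular index and of HRQoL, both collected under section 5.2.

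The cost is a sentence or two in section 9.1 and a few degrees of freedom in secondary models. No new data collection is needed if these doses are among those abstracted.

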### Power and sample size

We plan to enroll a total of 352 subjects, 176 of each sex), and assuming 10% drop out by the post-intervention 9-week assessment, we will have a total of 320 subjects (160 of each sex) remaining for evaluation. The

St Jude Children's Research Hospital

IRB NUMBER: 19-0121

IRB APPROVAL DATE: 05/04/2021

stratum, with 80 survivors per study arm, 80% power and  $\alpha$  of 0.05 for the primary endpoint comparison of the ISI, we will be able to detect a minimum effect size of 0.45. We will continue to enroll participants until we have 320 evaluable at 9 weeks. Assuming a total dropout of 20% by 6 months post-intervention, there will be approximately 70 survivors within each sex per study arm available for assessment, allowing detection of a 0.48 minimum effect size. If sex specific intervention effect estimates are comparable with each other, a combined analysis among the 320 survivors evaluable at 10 weeks will be sufficient to detect an effect size of 0.31, with 80% power and two-sided  $\alpha$  of 0.05. Secondary endpoints of neurocognition will have ability to detect the same effect sizes; secondary endpoint p-values will be presented using both a nominal significance level of 0.05 and adjustments for multiple comparisons using a false discovery rate methodology.

## 10.0 OBTAINING INFORMED CONSENT

### 10.1. Informed Consent Prior to Research Interventions

CCSS participants are recruited via email, telephone, and mail. Recruitment materials for this study will be included in the initial mailing and follow-up recruitment emails sent. Interested participants will be sent an email that contains a link to the study website. Participants will be presented with informed consent and will have the opportunity to provide an affirmative indication to enroll in the study. In addition to the on-line option to consent to participate in this study, participants will also have the opportunity to provide verbal consent while speaking with a representative from the CCSS Call Center.

## APPENDICES

### APPENDIX I: Schedule of Evaluations

Study Procedure	Time Point		
	Baseline	Post- Intervention	6 Month Follow-Up
Dried Blood Spot (DBS) Collection	X	X	X
Remote cognitive Assessment	X	X	X
CNS Vital Signs			
Drug Abuse Screen Test (DAST-10)	X		
Alcohol Use Disorders Identification Test (AUDIT)	X		
Insomnia Severity Index (ISI)	X	X	X
FACIT-Fatigue Questionnaire	X	X	X
Epworth Sleepiness Scale (ESS)	X	X	X
Childhood Cancer Neurocognitive Questionnaire (CCSS-NCQ)	X	X	X
Patient Health Questionnaire (PHQ-9)	X	X	X
Sleep Diary	X	X	X
WHOOP wrist monitor	X	X	X
Health-related Quality of Life Questionnaire	X	X	X
PROMIS Global Health	X	X	X
Work Productivity and Activity Impairment Questionnaire (WPAI)	X	X	X
Work and Social Adjustment Scale (WSAS)	X	X	X
